10.8.2 IMWG Consensus Criteria for Response and MRD in MM (Cohort E)

IMWG response criteria 2016 [Kumar, S., et al 2016].

Response assessments for Cohort E will be performed according to the IMWG criteria. The response assessment will include imaging assessments (including plasmacytoma and skeletal assessments), bone marrow results, MRD assessment, serum and urine protein results, serum FLC, and laboratory results.

Overall Response Category Definitions

IMWG MRD criteria (requires a CR as defined below):

- Sustained MRD-negative: MRD negativity in the marrow (NGF or NGS, or both) and by imaging as defined below, confirmed minimum of 1 year apart. Subsequent evaluations can be used to further specify the duration of negativity (eg, MRD-negative at 5 years).
- Flow MRD-negative: Absence of phenotypically aberrant clonal plasma cells by NGF on bone marrow aspirates using the EuroFlow standard operation procedure for MRD detection in multiple myeloma (or validated equivalent method) with a minimum sensitivity of 1 in 10^5 nucleated cells or higher.

- Sequencing MRD-negative: Absence of clonal plasma cells by NGS on bone marrow aspirate in which presence of a clone is defined as less than 2 identical sequencing reads obtained after DNA sequencing of bone marrow aspirates using the LymphoSIGHT platform (or validated equivalent method) with a minimum sensitivity of 1 in 10^5 nucleated cells or higher.
- Imaging plus MRD-negative: MRD negativity as defined by NGF or NGS plus disappearance of every area of increased tracer uptake found at baseline or a preceding PET/CT or decrease to less mediastinal blood pool SUV or decrease to less than that of surrounding normal tissue.

Standard IMWG response criteria

- Stringent CR: CR as defined below plus normal FLC ratio and absence of clonal cells in bone marrow biopsy by immunohistochemistry (κ/λ ratio $\leq 4:1$ or $\geq 1:2$ for κ and λ patients, respectively, after counting ≥ 100 plasma cells).
- Complete response: Negative immunofixation on the serum and urine and disappearance of any soft tissue plasmacytomas and $< 5\%$ plasma cells in bone marrow aspirates.
- Very good PR: Serum and urine M-protein detectable by immunofixation but not on electrophoresis or $\geq 90\%$ reduction in serum M-protein plus urine M-protein level < 100 mg per 24 h.
- Partial response:
 - $\geq 50\%$ reduction of serum M-protein plus reduction in 24 h urinary M-protein by $\geq 90\%$ or to < 200 mg per 24 h.
 - If the serum and urine M-protein are unmeasurable, a $\geq 50\%$ decrease in the difference between involved and uninvolved FLC levels is required in place of the M-protein criteria;
 - If serum and urine M-protein are unmeasurable, and serum-free light assay is also unmeasurable, $\geq 50\%$ reduction in plasma cells is required in place of M-protein, provided baseline bone marrow plasma cell percentage was $\geq 30\%$. In addition to these criteria, if present at baseline, a $\geq 50\%$ reduction in the size (SPD) of soft tissue plasmacytomas is also required.
- Minimal response: $\geq 25\%$ but $\leq 49\%$ reduction of serum M-protein and reduction in 24-h urine M-protein by 50–89%. In addition to the above listed criteria, if present at baseline, a $\geq 50\%$ reduction in the size (SPD) of soft tissue plasmacytomas is also required.
- Stable disease: Not recommended for use as an indicator of response; stability of disease is best described by providing the time-to-progression estimates. Not meeting criteria for CR, VGPR, PR, minimal response, or PD.
- Progressive disease: Any one or more of the following criteria:
 - Increase of 25% from lowest confirmed response value in one or more of the following criteria:
 - Serum M-protein (absolute increase must be ≥ 0.5 g/dL);

- Serum M-protein increase ≥ 1 g/dL, if the lowest M component was ≥ 5 g/dL; Urine M-protein (absolute increase must be ≥ 200 mg/24 h);
- In participants without measurable serum and urine M-protein levels, the difference between involved and uninvolved FLC levels (absolute increase must be >10 mg/dL);
- In participants without measurable serum and urine M-protein levels and without measurable involved FLC levels, bone marrow plasma cell percentage irrespective of baseline status (absolute increase must be $\geq 10\%$);
- Appearance of a new lesion(s), $\geq 50\%$ increase from nadir in SPD of >1 lesion, or $\geq 50\%$ increase in the longest diameter of a previous lesion >1 cm in short axis;
- $\geq 50\%$ increase in circulating plasma cells (minimum of 200 cells per μL) if this is the only measure of disease.

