- a) Have histologically or cytologically confirmed diagnosis of active MM as per IMWG criteria [Rajkumar, S. V., et al 2014].
b) Have measurable disease defined as meeting at least 1 of the following criteria:
c) Serum monoclonal protein (M-protein) levels ≥ 0.5 g/dL (≥ 5 g/L), OR
d) Urine monoclonal protein (M-protein) levels ≥ 200 mg/24 h, OR
e) For participants without measurable serum and urine M-protein levels, an abnormal serum-FLC ratio (FLC k/l < 0.26 or > 1.65) with involved FLC level ≥ 100 mg/L (normal serum FLC k/l value: 0.26-1.65).
f) Must have undergone stem cell transplant and have relapsed after auto-SCT or have failed to achieve a CR or PR following auto-SCT, or is considered ineligible for auto-SCT
g) Note: A planned treatment approach of induction therapy followed by auto-SCT, followed by maintenance, is considered one line of therapy.
h) Participants must have received all regionally approved antimyeloma therapy including IMiD (pomalidomide, lenalidomide, or thalidomide), proteasome inhibitor (bortezomib, carfilzomib, or ixazomib), steroids, anti-CD38 monoclonal antibody, selinexor, and anti-BCMA therapies alone or in combination.
i) Note: Exception in cases where an approved therapy is not available or not suitable for the participant.
j) Participants must have failed their last line of therapy, defined as 1 of the following:
i. Refractory: Nonresponsive (ie, failure to achieve at least PR) while on primary or salvage therapy, or documented progressive disease on or within 60 days of completing treatment, OR
ii. Relapsed: disease progression following prior response to antimyeloma therapy, participants must have relapsed within 6 months after stopping treatment.
Note: Participants must be relapsed or refractory to CAR-T-cell therapy or unable to receive it.

6. Cohort F: relapsed or refractory NHL

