5.2 Exclusion Criteria

The participant must be excluded from the study if the participant meets any of the following criteria:

Medical Conditions

1. For Cohort D and F (DLBCL and NHL): Has lymphoplasmacytic lymphomas, Waldenstrom's macroglobulinemia, chronic lymphocytic leukemia (not associated with small lymphocytic lymphoma), Burkitt (-like) lymphoma, mature T-cell and NK cell neoplasms, immunodeficiency associated lymphoproliferative neoplasms, or histiocytic and dendritic cell neoplasms.
2. For Cohort E (MM):
 - a) Has oligo-secretory myeloma, plasma cell leukemia, smoldering multiple myeloma, monoclonal gammopathy of undetermined significance.
 - b) History of primary amyloidosis, hyperviscosity or POEMS syndrome (plasma cell dyscrasia with polyneuropathy, organomegaly, endocrinopathy, monoclonal protein, and skin changes).
3. For Cohort F (EBV+ DLBCL): For patients with EBV+ DLBCL should NOT be associated with a solid organ transplant.
4. Has known prior or current CNS involvement.
5. A WOCBP who has a positive urine pregnancy test within 72 hours before study intervention allocation (see Appendix 5). If the urine test is positive or cannot be confirmed as negative, a serum pregnancy test will be required.

Note: If 72 hours have elapsed between the screening pregnancy test and the first dose of study intervention, another pregnancy test (urine or serum) must be performed and must be negative in order for participant to start receiving study medication.

6. Has clinically significant cardiovascular disease within 12 months from first dose of study intervention, including New York Heart Association Class III or IV congestive heart failure, unstable angina, myocardial infarction, cerebral vascular accident, or cardiac arrhythmia associated with hemodynamic instability.

Note: Medically controlled arrhythmia would be permitted.

7. Has a history or current evidence of any condition, therapy, or laboratory abnormality that might confound the results of the study, interfere with the participant's participation for the full duration of the study, or is not in the best interest of the participant to participate, in the opinion of the treating investigator.
8. Has a history of a second malignancy, unless potentially curative treatment has been completed with no evidence of malignancy for 3 years.

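### In Cohort E, a participant measurable only by free light chains can meet the printed VGPR definition at baseline, while the lower category PR requires a 50% light-chain fall

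*Combined protocol and SAP*

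**What the plan says.** Section 5.1 gives Cohort E three routes to measurable disease. The third reads "For participants without measurable serum and urine M-protein levels, an abnormal serum-FLC ratio" (outside 0.26 to 1.65), with involved FLC of at least 100 mg/L. For participants who enter this way, FLC is the qualifying measure of disease.

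Section 10.8.2 then defines response:

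- **Stringent CR:** "CR as defined below plus normal FLC ratio and absence of clonal cells in bone marrow biopsy by immunohistochemistry".
- **CR:** "Negative immunofixation on the serum and urine and disappearance of any soft tissue plasmacytomas", together with fewer than 5% "plasma cells in bone marrow aspirates". There is no FLC condition.
- **VGPR, first branch:** "Serum and urine M-protein detectable by immunofixation but not on electrophoresis". The second branch is a 90% serum M-protein reduction with a urine limit. Neither mentions FLC, marrow or plasmacytomas.
- **PR when M-protein is unmeasurable:** a 50% "decrease in the difference between involved and uninvolved FLC levels is required in place of the M-protein criteria".
- **PD:** "In participants without measurable serum and urine M-protein levels, the difference between involved and uninvolved FLC levels" is used, with a 25% increase and an absolute rise above 10 mg/dL.

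Section 9.4.1 counts CR and VGPR as objective responses in myeloma and points to Appendix 8 for the criteria. Section 9.1 requires myeloma responses to be confirmed on a second laboratory assessment in a row.

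**The concern.** The appendix recognises that M-protein cannot be followed in some participants and supplies a light-chain substitute, but only for PR and PD. The first VGPR branch is a condition a participant can be in, not a change from baseline. In an FLC-only participant it can hold before the first dose. Confirmation does not help, because an unchanged result confirms itself. The higher response category is then easier to reach than the lower one, which is a contradiction within the appendix.

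At stake are Cohort E's ORR, the DOR analysis (which such a participant would enter as a responder) and, to a lesser degree, DCR. Section 4.1.1 plans a futility review after 12 participants per cohort, and Section 4.1.2 bases the opening of Part 2 on benefit and risk by disease type. Table 7 reports no confirmed response among 30 myeloma participants on pembrolizumab alone. Against that context, one or two responses could be read as a signal.

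**Working it through.** **Inputs.** n = 30 per cohort and a 95% exact interval (Section 9.9); 12 participants at the futility review (Section 4.1.1); response definitions (Section 10.8.2); entry route (Section 5.1). The number of FLC-only participants is not given.

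**Step 1: the plan's own figure.** Clopper-Pearson limits are lower = Beta(0.025; x, n−x+1) and upper = Beta(0.975; x+1, n−x). Over x = 0 to 30 with n = 30, the half-width is largest at x = 15 and equals 18.70%. This agrees with the 18.7% in Section 9.9.

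**Step 2: follow an FLC-only participant whose disease does not change.**

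- *VGPR:* if immunofixation is positive and electrophoresis negative in serum and urine at baseline, the first branch is met at baseline. Two unchanged tests confirm it, and Section 9.4.1 counts it.
- *PR:* a fall of at least 50% in the FLC difference is required. The observed fall is 0%, so PR is not met.
- *PD:* a 25% rise with more than 10 mg/dL absolute increase is required. It is not met, so PD does not block the VGPR. A stable FLC, or one falling by less than 50%, leaves this participant at VGPR.
- *CR:* without any fall, this needs negative immunofixation, no plasmacytoma and marrow plasma cells already below 5%, all at baseline. Section 5.1 prints no minimum marrow percentage, so this is not strictly excluded, but it is a far narrower route.

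**Step 3: DCR.** In Section 9.4.1 the 12-week duration attaches to stable disease, while VGPR counts once achieved. An unchanged participant who stays stable for 12 weeks counts in DCR anyway. The VGPR label therefore alters DCR only for those who progress sooner. Section 3 can be read as applying the 12 weeks to every category, which would remove even that effect.

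**Step 4: effect on ORR.** Each false responder adds 1/30 = 3.3 points.

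- 0/30: 0% (0 to 11.6)
- 1/30: 3.3% (0.1 to 17.2)
- 2/30: 6.7% (0.8 to 22.1)
- 3/30: 10.0% (2.1 to 26.5)

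At 12 participants, one is 1/12 = 8.3 points.

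**Step 5: how often, under assumptions.** Let f be the FLC-only share and q the share of those who meet the first VGPR branch at baseline. Neither is in the documents. The expected number of false responders is 30fq, and the chance of at least one among n is 1−(1−fq)^n.

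- f = 5%, q = 25%: 30 × 0.0125 = 0.4 expected; 31% in 30; 14% in 12.
- f = 10%, q = 50%: 30 × 0.05 = 1.5 expected; 79% in 30; 46% in 12.
- f = 20%, q = 100%: 30 × 0.20 = 6 expected; above 99% in 30; 93% in 12.

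**The case against.** The strongest reply is that Appendix 8 summarises a standard. Section 10.8.2 says Cohort E is assessed by the cited IMWG 2016 criteria, and those may contain the missing light-chain rules. Table 15 also refers to Section 8.2, which is redacted, so nothing can be called absent from there. This stands as a limit: the documents do not show that the trial will score false responders. It does not remove the contradiction. Section 9.4.1 sends the scorer to Appendix 8, which prints full definitions with a light-chain substitute for some categories and not others. A site could reasonably conclude that none applies to VGPR or CR.

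The route is also narrower than it first looks. Unmeasurable M-protein means below the entry thresholds (0.5 g/dL in serum, 200 mg/24 h in urine), not invisible on electrophoresis. A participant with a small visible spike, or one who is immunofixation-negative, does not meet the first branch at baseline. Read literally, the branch needs detection in both serum and urine. Section 9.4.1 speaks of achieving a response, which sits awkwardly with an unchanged state. These points reduce the number affected, but they do not close the gap.

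Section 5.2 excludes a participant who "Has oligo-secretory myeloma, plasma cell leukemia, smoldering multiple myeloma, monoclonal gammopathy of undetermined significance". The first term is undefined there and does not cancel the explicit FLC-only entry route.

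A reader might infer that CR can be scored whatever the light chains do. The documents do not support that. A sufficient FLC rise is PD, and the marrow and plasmacytoma conditions will usually require a real fall.

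**Conclusion.** The point holds, resting on VGPR. As printed, FLC-only participants who are immunofixation-positive and electrophoresis-negative at baseline meet VGPR with no fall in disease, while PR needs a 50% fall in the FLC difference. CR shares the missing light-chain condition, but it is guarded by immunofixation, plasmacytoma and marrow. Rising FLC is caught by the PD rule; stable or insufficiently falling FLC is not.

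The size is 3.3 ORR points per false responder in 30. How many there would be is unknown, and the range in Step 5 rests on assumed shares. The effect is confined to Cohort E, where ORR is a secondary endpoint estimated without a hypothesis test. The 0/30 in Table 7 is context, not a comparator. The futility rule is redacted, so its sensitivity to one extra responder cannot be judged.

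A reader might also link this to the option in Section 6.1.1 to stop treatment after CR. That section requires confirmation of CR in myeloma and at least 8 further cycles, and the defect shown here lies mainly in VGPR. No argument is made on that ground.

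**What to change.** In Section 10.8.2, for participants measurable only by FLC at baseline:

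1. Score VGPR or CR only if the PR light-chain condition is also met (a fall of at least 50% in the involved-minus-uninvolved difference).
2. Require a normal FLC ratio for CR, using the 0.26 to 1.65 range already in Section 5.1.
3. Print an FLC-difference threshold for VGPR taken from the cited IMWG criteria. A fall of at least 90% would mirror the printed M-protein rule, but that figure is an analogy and is not given in the documents for FLC, so it should be checked against the source.
4. State that these rules govern response scoring.

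The cost is a few sentences in Appendix 8. Serum FLC is already listed there as part of the response assessment, so the change calls for no new type of data. The sample size and the 18.7% half-width do not change. The Cohort E ORR may come out slightly less favourable.

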10.9 Appendix 9: Eastern Cooperative Oncology Group Performance Status

Grade	Performance Status
0	Normal activity. Fully active, able to carry on all predisease performance without restriction.
1	Symptoms, but ambulatory. Restricted in physically strenuous activity, but ambulatory and able to perform work of a light or sedentary nature (eg, light housework, office work).
2	In bed <50% of the time. Ambulatory and capable of all self-care, but unable to carry out any work activities. Up and about more than 50% of waking hours.
3	In bed >50% of the time. Capable of only limited self-care, confined to bed or chair more than 50% of waking hours.
4	100% bedridden. Completely disabled. Cannot carry on any self-care. Totally confined to bed or chair.
5	Dead

Adapted from [ECOG ACRIN Cancer Research Group 2016]

10.10 Appendix 10: Abbreviations

Abbreviation	Expanded Term
ADA	antidrug antibodies
ADR	adverse drug reaction
AE	adverse event
AEOSI	adverse event of special interest
ALK+	anaplastic lymphoma kinase-positive
ALT	alanine aminotransferase
APaT	All Participants as Treated
AST	aspartate aminotransferase
AUC	area under the curve
BM	bone marrow
CAR	Chimeric antigen receptor
CD	cluster of differentiation
cHL	classical Hodgkin's Lymphoma
CI	confidence interval
CL	clearance
Cmax	maximum plasma concentration
CMR	complete metabolic response
CNS	central nervous system
CONSORT	Consolidated Standards of Reporting Trials
CR	complete response
CRF	Case Report Form
CSR	Clinical Study Report
CT	computed tomography
CTCAE	Common Terminology Criteria for Adverse Events
ctDNA	circulating tumor DNA
CTLA-4	cytotoxic T-lymphocyte-associated protein 4
C _{trough}	lowest plasma concentration
DCR	Disease control rate
DLBCL	Diffuse Large B-cell lymphoma

Abbreviation	Expanded Term
DLT	dose-limiting toxicity
DLTe	dose-limiting toxicity evaluable
DNA	deoxyribonucleic acid
DOR	duration of response
EBV	Epstein Barr virus
EC	Ethics Committee
ECG	electrocardiogram
ECI	event of clinical interest
eCRF	electronic Case Report Form
ECOG PS	Eastern Cooperative Oncology Group Performance Score
EDC	electronic data collection
ELISA	enzyme-linked immunosorbent assay
EMA	European Medicines Agency
EORTC	European Organization for the Research and Treatment of Cancer
ePROs	electronic patient-reported outcomes
EQ-5D-5L	EuroQoL 5D-5L
EuroQoL	European quality of life
FBR	future biomedical research
Fc γ R	Fc-gamma receptor
FDAAA	Food and Drug Administration Amendments Act
FDG	fluorodeoxyglucose
FISH	fluorescent in situ hybridization
FL	Follicular Lymphoma
FLC	free light chain
FLIPI	Follicular Lymphoma International Prognostic Index
FOXP3	forkhead box P3 protein
FSH	follicle-stimulating hormone
GCP	Good Clinical Practice
GVHD	graft versus host disease
HBsAg	hepatitis B surface antigen

Abbreviation	Expanded Term
HBV	hepatitis B virus
HCV	hepatitis C virus
HIV	human immunodeficiency virus
HL	Hodgkin's Lymphoma
HRQoL	health-related quality of life
HRT	hormone replacement therapy
IB	Investigator's Brochure
ICF	Informed Consent Form
ICH	International Council for Harmonisation of Technical Requirements for Pharmaceuticals for Human Use
ICMJE	International Committee of Medical Journal Editors
ICR	independent central review
ID	identification
IEC	Independent Ethics Committee
IFN- γ	interferon-gamma
Ig	immunoglobulin
IgG4	immunoglobulin G4
IHC	immunohistochemistry
IMiD	immunomodulatory drugs
IMP	investigational medicinal product
IMWG	International Myeloma Working Group
IND	Investigational New Drug
IO	immuno-Oncology
IPI	International Prognostic Index
irAEs	immune-related AEs
IRB	Institutional Review Board
IUD	intrauterine device
IUS	intrauterine hormone-releasing system
IV	intravenous
IVD	in vitro diagnostic
LAG	lymphocyte activation gene

Abbreviation	Expanded Term
LAM	lactational amenorrhea method
LDi	longest diameter
mAb	monoclonal antibody
MCL	Mantle Cell Lymphoma
MIPI	Mantle Cell Lymphoma International Prognostic Index
MIPI-c	MIPI + Ki-67 index
MM	Multiple Myeloma
mPD-1	murine programmed cell death 1 protein
MR	Minor response
MRD	minimal residual disease
MRI	magnetic resonance imaging
mRNA	messenger RNA
MSI	microsatellite instability
MTD	maximum tolerated dose
mTIGIT	murine TIGIT
MYC	myelocytomatosis
MZL	marginal zone lymphoma
n	number
NCI	National Cancer Institute
NGF	next generation flow
NGS	next generation sequencing
NHL	Non-Hodgkin's Lymphoma
NK	natural killer cell
NKT	natural killer T-cell
NOS	not otherwise specified
NSCLC	non-small cell lung cancer
ORR	objective response rate
OS	overall survival
OTC	over-the-counter
PBMC	peripheral blood mononuclear cells

Abbreviation	Expanded Term
PBPK	Physiologically based PK
PD	progressive disease
PD-1	programmed cell death 1 protein
PD-L1	programmed cell death ligand 1
PD-L2	programmed cell death ligand 2
PET	positron emission tomography
PFS	Progression-free survival
PI3K	phosphoinositide 3-kinase
PK	pharmacokinetic
PMBCL	Primary mediastinal B-cell lymphoma
PO	by mouth
PPD	product of perpendicular diameters
PR	partial response
PRN	as needed
PRO	patient-reported outcome
PVRL-2	poliovirus receptor-related 2
Q2W	every 2 weeks
Q3W	every 3 weeks
Q12W	every 12 weeks
Q24W	every 24 weeks
QLQ	quality of life questionnaire
QoL	quality of life
RECIST	Response Evaluation Criteria In Solid Tumors
RNA	ribonucleic acid
SAE	serious adverse event
SAP	Statistical Analysis Plan
SCT	stem cell transplant
SD	stable disease
SDi	short axis diameter
SLL	Small Lymphocytic Lymphoma

Abbreviation	Expanded Term
SNP	single-nucleotide polymorphism
SoA	schedule of activities
SPD	sum of the product of diameters
SPEP	serum protein electrophoresis
sSAP	supplemental Statistical Analysis Plan
SUSAR	suspected unexpected serious adverse reaction
SUV	standardized uptake value
SUVmax	maximum standardized uptake value
T3	Triiodothyronine
T4	Thyroxine
TIGIT	T-cell immunoreceptor with Ig and ITIM domains
TILs	Tumor-infiltrating lymphocytes
TIM-3	T-cell immunoglobulin and mucin-domain containing-3
TNF	Tumor necrosis factor
TPS	Tumor proportion score
T-reg	Regulatory T-cell
TSH	Thyroid-stimulating hormone
ULN	upper limit of normal
UPEP	urine protein electrophoresis
US	United States
VAS	Visual Analog Scale
Vc	central volume of distribution
VGPR	very good partial response
WHO	World Health Organization
WOCBP	woman/women of childbearing potential

